#### 5.3.2 Persons with Dementia

We will seek to obtain de-identified data (with exception of dates of service and zip codes) of PWD who receive care from the hospices who participate in the study in order to determine the fidelity of the study ([See milestone 3 above](#)). We will seek a waiver of consent and authorization for this population as NYU will not be performing

CONFIDENTIAL

This material is the property of the NYU School of Medicine and Langone Medical Center. Do not disclose or use except as authorized in writing by the study sponsor

Interventional Template Version: 3.28.19

any research directly with this population. The only contact between the PWD/surrogate in this study would be to perform informed consent, and would not be practical given the dispersed nature of the subject population and number of subjects we'd have to contact. In addition to IRB approval, a Data Use Agreement will be executed to obtain this data.

#### **5.4 Total Number of Participants and Sites**

An estimated 400 clinicians and 200 PWD will serve as participants at the two hospice agencies.

#### **5.5 Participant Withdrawal or Termination**

##### **5.5.1 Reasons for Withdrawal or Termination**

Given the nature of the study, we do not see any reason a PWD would withdraw as they would not be actively participating in research and only their de-identified data other than dates of service and zip codes provided to the investigators.

Regarding clinician subjects, the primary reason for withdrawal would be leaving employment or not completing the online training.

Clinician subjects are free to withdraw from participation in the study at any time upon request. An investigator may terminate participation in the study if:

- The subject is unable to complete training or the individual leaves the hospice agency during the time period of the study.

##### **5.5.2 Handling of Participant Withdrawals or Termination**

Given the minimal risk nature of this study, should individuals choose to withdraw from the study, we will not continue to follow-up or follow them in any form.

### **6 Study Quality Improvement Program**

#### **6.1 Study Behavioral or Social Quality Improvement Program**

The DSM-H Hospice Edition as described in [section 2.2](#) is a quality improvement program that has been adapted from and heavily based on the pre-existing DSM-H HHC edition. The adaptation took into account regulatory and clinical team differences between the two. The original DSM-H was tested in several HHC agencies in New York and the hospice edition's educational components were tested with a nationwide sample of hospice social workers. The DSM-H Hospice edition is a multi-modal quality improvement program for improving the quality of care provided to PWD-informal caregiver dyads through hospice. The initial DSM-H home health edition training was initially created through participatory research with an interprofessional team of clinicians, and then refined through feedback from clinicians who completed the training. It has been culturally tailored for use in diverse settings and tested with multiple minority communities in New York, including multiple Hispanic groups and African-Americans and Caribbean blacks. This new hospice edition is based on the prior home health edition. The DSM-H Hospice Edition quality improvement program presented in this section is not in and of itself a study intervention. We are solely in this study measuring the outcomes of the quality improvement program, however include the components of the program here so it is easier to understand the research protocol around the study of outcomes.

##### **6.1.1 Procedures for Training Quality Improvement Teams and Monitoring Fidelity**

Because there are multiple care teams receiving the performance improvement program, and we need to understand how well the program is implemented in order to assess the research outcomes, we will measure

CONFIDENTIAL

This material is the property of the NYU School of Medicine and Langone Medical Center. Do not disclose or use except as authorized in writing by the study sponsor

fidelity of implementation (e.g. clinician exposure to the performance improvement program) as well as differences across control and performance improvement teams through assessing registered nurse, physical and occupational therapist knowledge, attitudes and confidence using [name] previously validated dementia symptom knowledge and attitudes survey at baseline, 3 months, and 1 year2, and through measuring the number of care plans initiated, caregiver teaching sheets provided to caregivers, and assessment instruments used at each site throughout the trial.

## 7 Study Procedures and Schedule

### 7.1 Study Procedures/Evaluations

#### 7.1.1 Study Specific Procedures

##### 7.1.1.1 Clinician Knowledge, Confidence, Attitudes

We will implement the DSM-H Hospice Edition first at MJHS, then make iterative changes for usability and applicability based on feedback from our stakeholder workgroup and the MJHS hospice participants, and implement at Providence Trinity Hospice.

To assess knowledge of the clinicians, the DSKA (skilled clinicians) or HHA assessment (hospice aides) will be collected prior to and post online training via Qualtrics survey. It takes approximately 15 minutes to complete the former and 10 minutes the latter. The DSKA includes baseline demographics (first survey only for an individual) and 79 likert style items regarding their knowledge, confidence and attitudes towards pain, depression and behavioral symptom assessment and management in persons with dementia. We have administered, and clinicians have completed the DSKA hundreds of times in the past four years in intervention and control settings and it has a Cronbach Alpha of .94.

The HHA assessment takes approximately 10 minutes to complete and following demographic also includes 17 true false and likert style questions regarding knowledge and confidence in managing care tasks in PWD. We have administered this survey to over 1100 HHA in the past two years and it has strong internal consistency and validity.

##### 7.1.1.2 Optional Professional Quality of Life

We will implement the professional quality of life survey at pilot site 2 to assess professional quality of life of the clinicians before and after DSM-H hospice training. It takes approximately 10 minutes to complete the surveys. The survey instruments include the professional quality of life (ProQOL-5), which is a 30 question self-report questionnaire measuring professional quality of life on a 5-point Likert scale. about how frequently the participant experienced the things being asked about in the last 30 days. The scale starts at one indicating never and goes to five indicating very often. It measures professional quality of life on three subscales including compassion satisfaction, burnout and secondary traumatic stress. Higher scores on the burnout and secondary traumatic stress indicate higher risk for burnout and higher secondary traumatic stress, respectively. Higher scores on the compassion satisfaction scale indicate greater satisfaction in your ability to be an effective caregiver at your job. A 9-item Well-being Index (WBI) will be used to identify U.S. workers in distress and stratify quality of life. The WBI is a successful screening tool to identify distress and identify those with high well-being among nurses and among a variety of workers.  Supplemental questions asked will be taken from the National Sample Survey of Registered Nurses question numbers: 36, 66, 67. The last question included is a retention question that asks: "Do you plan to be with your employer one year from now?" Yes or No.

##### 7.1.1.3 Applicability to the setting

In addition to asking clinicians and hospice aides about their knowledge, confidence and attitudes, we will also ask them about the applicability of the program through a series of questions via the online survey (see questions under other materials).

CONFIDENTIAL

This material is the property of the NYU School of Medicine and Langone Medical Center. Do not disclose or use except as authorized in writing by the study sponsor

We will also perform a focus group with all champions who consent to participate. The focus group will be held in the same room where the champion training was performed at the end of that day and will take approximately 20 minutes to complete. The focus group will ask three open ended questions about the champions training, with follow-up questions based on response. These questions are: what did you feel were the best parts of the champion training and why; what did you feel were the parts you liked least about the champion training and why; how do you think it will help you change the practice of clinicians in your agency; what would you change about the champions training?

### **7.1.2 Standard of Care Study Procedures**

PWD subjects who are in the control group will receive usual care as provided by the hospice agency.

## **7.2 Study Schedule**

### **7.2.1 Screening**

The NYU study team will be provided a list of all staff by the hospice agency who are in the applicable care teams at the participating hospices. We will then invite them to take part in this research study consisting of pre- and post-training survey assessments. The initial survey will ask them the eligibility questions at the beginning following review of the consent document, and should they not click the eligible options will be directed to the end of survey where a message will be performed stating they are not eligible. All eligible clinician subjects will continue on to the remainder of the pre-training survey assessment.

### **7.2.2 Pre-Training Assessment**

At baseline the HHA will take the HHA assessment, and skilled clinicians will take the DSKA assessment. They will then at completion receive access to their respective training modules. Champions will be scheduled to take the in-person training together.

### **7.2.3 Post-Training Assessment**

Following completing the online training modules, the clinician subjects will proceed to the appropriate post-training assessment.

### **7.2.4 Collection of Hospice Record**

Following completion of the pilot, we will collect de-identified data of eligible PWD other than zip codes and dates of service. This is pre-existing routinely collected data by the agencies of all PWD who are receiving care at the participating hospice agencies. We will primarily be looking to describe the population as well as determine how many assessment instruments or care plans have been initiated, and types and frequency of symptoms, and pharmacologic and non-pharmacologic interventions utilized.

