#### **4.1.3 Aim 3: Pilot test the complete protocol and DSM-H Hospice Edition in 2 hospice agencies and refine further based on feedback from the pilot agencies.**

*Pilot testing the revised DSM-H Hospice Edition.* Following revision, we will perform a pilot implementation in 3 IDTs at MJHS Hospice and Palliative Care, a large local hospice that serves a diverse patient population across New York City and Long Island.

Testing the refined intervention components for skilled IDT members. We will test the components of the refined intervention for skilled IDT members. We will perform a summative evaluation through pre-post testing using the DSKA, which has established content and face validity and internal consistency to measure the intervention's effects on knowledge, confidence and attitudes. We will also perform a formative evaluation with completers regarding the applicability of the content through both quantitative and qualitative survey feedback. Data will be collected in Qualtrics survey software. We will also conduct a short focus group with champions to obtain feedback on the revised champion training. For this focus group we will use field notes rather than recording, as the goal is not to perform a thorough scientific qualitative analysis but obtain feedback on what did and did not work in terms of applicability, relatability to the IDT and implementability. The Focus groups and DSKA are being used for program evaluation and not research.

CONFIDENTIAL

Testing the online HHA training for usability and applicability. Second, we will evaluate HHA knowledge and confidence, using the same tool we used in its initial development, to ensure that the effect of the online program is at least as good as in person program. We will also complete a standard systematic usability evaluation through anonymized screen recording, analyzing answers to embedded questions within the modules, and a formative evaluation by users (i.e., HHA who complete and do not complete the program).

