## 5 Study Enrollment

### 5.1 Inclusion Criteria

CLINICIANS/AIDES; All English speaking interdisciplinary team (IDT) members employed or contracted by the agency who are receiving DSM-H online or champion training greater than 18 years of age will be eligible.

PWD: All PWD who are newly admitted to a participating hospice during the timeframe following implementation of the intervention who are over the age of 50 will be eligible.

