### **10.3 Analysis Datasets**

We will maintain separate data sets nested by site for skilled clinicians, hospice aides, and PWD.

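### At the first agency the programme goes into 3 care teams, but patients are counted hospice-wide with no team code, so any untrained teams' patients would dilute the care-plan and instrument proportion

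*Combined protocol and SAP*

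**What the plan says.** **Delivery is by team.** Section 4.1.3 states that "we will perform a pilot implementation in 3 IDTs at MJHS Hospice and Palliative Care, a large local hospice".

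**Staff are scoped to match.** Section 7.2.1 lists for invitation those "who are in the applicable care teams at the participating hospices".

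**Patients are scoped to the hospice.** Section 5.1 makes eligible "All PWD who are newly admitted to a participating hospice during the timeframe following implementation of the intervention", subject to an age limit but with no criterion on the treating team. Section 5.3.2 seeks data on people with dementia cared for by the participating hospices, expressly to determine fidelity, and points to milestone 3. Section 7.2.4 says "we will collect de-identified data of eligible PWD other than zip codes and dates of service", and then adds: "This is pre-existing routinely collected data by the agencies of all PWD who are receiving care at the participating hospice agencies".

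**No team level is planned in the data.** Section 10.3 says "We will maintain separate data sets nested by site for skilled clinicians, hospice aides, and PWD". No team identifier is named for patients.

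**Where the figure is used.** Section 4.1.3 sends first-pilot data to the work groups for possible refinement, then repeats the same testing at a second agency without saying how many of its teams are trained. Section 4.2.1 judges the 75% fidelity milestone at the second agency.

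**Control text.** Sections 6.1.1 and 10.4.2 mention comparisons of control teams with programme teams, and 7.1.2 mentions a patient control group on usual care. None of these is defined. The Protocol Summary calls the study pre-post.

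**The concern.** The unit that receives the programme (the team) and the unit that defines the patient sample (the hospice) do not match. The main patient-level measure is the proportion of patients with at least one care plan or assessment instrument used. Its purpose is to show whether the programme was put into practice where it was delivered. Counted over a whole agency in which only some teams are trained, it blends implementation with ordinary practice and understates uptake wherever untrained teams use the tools less.

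The protocol itself treats adherence as a care-team matter (10.4.2), but an extract without a team field cannot support a team-level reading. First-pilot data feed decisions on refining the intervention, its implementation and its measurement. A diluted figure could there be taken for weak uptake. The descriptions of symptoms and treatments listed in 7.2.4 would be mixed in the same way.

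**Working it through.** There is no planned figure to reproduce. The 200 patients and 400 clinicians in 5.4 are estimates for a convenience sample (10.5), with no split by agency or team. The check is therefore first of the text, then of the possible size.

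**Step 1: does any wording limit patients to trained teams?**
- Section 7.2.4 collects data on eligible patients, so its next sentence need not mean literally every patient.
- Eligibility comes from 5.1, which is also hospice-wide: "All PWD who are newly admitted to a participating hospice during the timeframe following implementation".
- Section 5.3.2 defines the fidelity source at hospice level too.
- Section 10.3 stops at site.

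Nothing restores a team restriction.

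**Step 2: are there untrained teams?** The count of 3 IDTs, the description of the hospice as large, and the reference to applicable care teams all imply it. No section gives the total, so it is an assumption here.

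**Step 3: size of the dilution.** Let k be the number of IDTs, t the use in trained teams and u the use in the others, with equal caseloads. None of k, t, u or the caseload split is in the documents.

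Agency figure = (3/k) × t + (1 − 3/k) × u

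With t = 0.85 and u = 0.10:
- k = 6: 0.5 × 0.85 + 0.5 × 0.10 = 0.475
- k = 10: 0.3 × 0.85 + 0.7 × 0.10 = 0.255 + 0.070 = 0.325

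The same formula over a range of u, with t = 0.85:

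| IDTs (k) | u = 10% | u = 30% | u = 50% |
|---|---|---|---|
| 3 (all trained) | 85% | 85% | 85% |
| 4 | 66.25% | 71.25% | 76.25% |
| 6 | 47.5% | 57.5% | 67.5% |
| 10 | 32.5% | 46.5% | 60.5% |

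The shortfall is (1 − 3/k) × (t − u). It is zero if every team is trained, and it shrinks as untrained use approaches trained use.

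**Step 4: does it reach the milestone?** Only if the second agency is partly trained. In that case, the share of its patients that must be under trained teams for the pooled figure to reach 75% is (0.75 − u)/(t − u). With t = 0.85:
- u = 0.10: 0.65/0.75 = 0.867
- u = 0.30: 0.45/0.55 = 0.818
- u = 0.50: 0.25/0.35 = 0.714

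If all teams there are trained, the share is 1 and there is no dilution.

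**The case against.** **The lead sentence of 7.2.4 may describe the source, not the scope.** It can be read as saying where the records come from, and the sentence before it limits collection to eligible patients. That is a fair reading, but 5.1 and 5.3.2 are hospice-wide as well, so the point stands without it.

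**The threshold is at the other agency.** This stands. A reader might infer that the progression decision is compromised. The documents do not support that: 4.2.1 judges the milestones at the second agency, and 4.1.3 describes that pilot at a hospice with a smaller census without mentioning a subset of teams.

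**Untrained teams may not have low use.** This also stands. The instruments are built into the electronic health record (2.2.4), all medical providers take a training module (2.2.2), and champions are to lead change across their agency (2.2.1). The gap between trained and untrained teams could be small.

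**A comparator is not lost.** A reader might infer that the plan throws away a concurrent usual-care group. It does not. An agency-wide extract would contain those patients; what is missing is the means to identify them and a plan to report them. Nor is a comparison an aim of this phase: 10.2 states no hypotheses, 8.2 rules out monitoring of effectiveness, and 4.1.3 already collects the month before implementation.

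**The harm is speculative.** The first-pilot patient data mainly test collection and merging, and the work groups would know that only 3 IDTs took part. This lowers the risk of misreading. It does not give them the trained-team figure, which they could not recover without a team field.

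**Conclusion.** The mismatch holds and can be read directly from the text: implementation in 3 IDTs, clinicians limited to the applicable teams, patients defined for the whole hospice, and no team identifier. If other IDTs exist at the first agency, their patients enter the care-plan and instrument proportion, pull it towards usual care, and cannot be taken out afterwards.

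The size cannot be fixed from the documents. Under the assumptions shown, 85% use in trained teams would read anywhere from 32.5% (10 IDTs, 10% use elsewhere) to 76.25% (4 IDTs, 50% use elsewhere), and 85% if all teams are trained. The effect is on the first pilot's description and refinement step. Any effect on the 75% milestone depends on partial training at the second agency, about which the protocol is silent. This is a worthwhile clarification because it is cheap, not because the pilot's main decision has been shown to be at risk.

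**What to change.** - In 5.1, 5.3.2 and 7.2.4, define the fidelity set as patients whose assigned IDT received the programme.
- Add a de-identified team code and a trained yes/no flag to the extract. Section 4.1.3 leaves the transfer specification open to refinement, so this is the time to add them. Extend 10.3 to show team within site.
- Compute the care-plan and instrument proportion in the fidelity set. State how many of the second agency's teams are trained and, if only some are, compute milestone 3 in the same set.
- Patients of any non-implementing teams may be shown separately for the same months, as description only, with a note on possible contamination through shared record tools, providers and champions.
- Define or remove the control-group text in 6.1.1, 7.1.2 and 10.4.2 so that it agrees with the pre-post design in the Protocol Summary.

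The cost is a small addition to the data request (the team code with its flag), some rewording, and a smaller analysis set with correspondingly less precision.

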### **7.2.5 Withdrawal/Early Termination Visit**

Clinician subjects can withdraw from the study at any time, and will not have to complete the assessment instruments, though they may be required by the hospice agency to complete the training as an operational initiative.

CONFIDENTIAL

This material is the property of the NYU School of Medicine and Langone Medical Center. Do not disclose or use except as authorized in writing by the study sponsor  
Interventional Template Version: 3.28.19

## 8 Assessment of Safety

### 8.1 Staff (Clinicians)

There is minimal risk to the healthcare staff as the content is not sensitive in nature and the surveys do not significantly relate to measures on which staff are measured for job accountability. The greatest risk to staff is the loss of confidentiality. We will not share any data collected back to the agency. For reporting purposes in conference proceedings, abstracts and manuscripts, data will be aggregated to ensure lack of identifiability to the staff level.

### 8.2 Persons with Dementia

We will not be monitoring efficacy or effectiveness during the R61 pilot phase of this evidence-based practice intervention, and therefore will not be actively monitoring for adverse events.

#### 8.2.1 Data Safety and Monitoring

The Principle Investigator will ensure overall safety of the subjects in the R61 pilot phase on a daily basis and will be responsible for all reporting. The study statistician will be responsible for running reports on data safety, consistency and outcomes and reviewing them with the study PI.

#### 8.2.2 Frequency and Reporting

As this is a R61 pilot and not a clinical trial, and outcomes are around feasibility, acceptability and fidelity, we will not perform routine reporting other than the annual continuing review. If we find through our analyses any negative outcomes the PI will report them within 24 hours to the IRB and NIH program officer.

